## *Adverse Events of Specific Interest (AESI)*

Adverse events of particular clinical importance (other than SAEs mentioned above) will be classified as adverse events of specific interest (AESIs). For this study, AESIs refer to:

- Mild/moderate reactions:

- Skin blisters
- Wound bleeding
- Allergic skin reaction

### *Assessing and Documenting Reportable Events:*

Subjects will be evaluated for adverse events in the following manner:

- Routine monitoring by physicians, nurses and research team during inpatient stay, with data obtained from the subject's EMR by research staff.
- Typically patients will be scheduled for routine follow-up with their provider at 1-2 weeks and 4-6 weeks postpartum
- Research staff will call subjects on postoperative day 30 ( $\pm 2$  days) and will ask patients standardized questions regarding wound complications. Medical records will be obtained for any patient or provider-reported complications.

An adverse event report will be generated for each event that will include the following:

- Date of event discovery
- Severity (mild, moderate, severe, life threatening/disabling, death)
- Relationship to treatment
- Action taken
- Outcome
- Expected or unexpected
- Date reported
- Relevant notes/chart records/supporting documentation to corroborate the event
- To whom event was reported (IRB, Sponsor)

- **Non-Severe AESI will be reported to the lead site as aggregate every 6 months, and to the IRB at renewal.**
- **SAEs will be reported within 24 hours of discovery to the IRB and the lead site.**

*Relationship of Reportable Events:*

An Investigator must make the determination of relationship to the drug for each SAE and/or AESI.

The relationship to the drug or device should be assessed using the guidelines presented in the table below.

Relationship to Device	Description
Related	

• Previously known harmfulness of device; or

• Follows a reasonable temporal sequence from administration of the device; or

• Follows a known or expected response pattern to the suspected intervention; or

• Is confirmed by stopping or discontinuing the device; and

• That is not explained by any other reasonable hypothesis

Probably related	

• Follows a reasonable temporal sequence from the time of study intervention; and/or

• Follows a known response pattern to the study device; and

• Was unlikely to have been produced by other factors such as the subject's clinical state, therapeutic intervention, or concomitant therapy

Possibly related	

• Follows a reasonable temporal sequence from the time of study intervention; and/or

• Follows a known response pattern to the study device; but

• Could have been produced by other factors such as the subject's clinical state, therapeutic intervention, or concomitant therapy

Unlikely related	

• Does not follow a reasonable temporal sequence from the time of study intervention; and

• Was likely produced by other factors such as the subject's clinical state, therapeutic intervention, or concomitant therapy but for which relationship cannot be definitely ruled out

Not related	The adverse event can be determined with certainty to have no relationship to the study device

*Severity of Reportable Events:*

The investigator will assess the severity of the AE using the following general guidelines:

Severity	Description
Mild:	An AE that is usually transient, requiring no special treatment, and does not interfere with the subject's daily activities.
Moderate:	An AE that introduces a low level of inconvenience or concern to the subject and may interfere with daily activities but is usually ameliorated by simple therapeutic measures.
Severe:	An AE that interrupts a subject's usually daily activity and typically requires systemic drug therapy or other treatment (a severe AE may not necessarily qualify as an SAE).
Life-threatening:	An AE that put the subject at immediate risk of death from the event as it occurred. This does not include an event that might have led to death if it had occurred with greater severity.

### *Outcomes of Reportable Events:*

The investigator will categorize the outcome of each reportable event according to the definitions below:

Status	Description
Resolved:	The subject recovered from the SAE or AESI.
Resolved with sequelae:	A condition whereby the consequences of a disease or injury include lingering effects.
Ongoing:	At the time of the last assessment, the event is ongoing, with an undetermined outcome. Note: Ongoing SAEs and AESIs are not considered resolved as a result of death and no SAE or AESI stop date should be recorded for an AESI that is ongoing at the time of death.
Fatal:	Adverse Event directly caused death. If a subject dies during participation in the study the lead site should be provided with a copy of any post-mortem findings. Note: Death is an outcome of an adverse event and not an adverse event in itself. All reports of subject death should include an adverse event term (other than "Death") for the cause of the death.

## *Data Monitoring and Quality Control*

Periodic monitoring visits will be made at the investigational site throughout the clinical study to ensure that the investigator obligations are fulfilled, and all applicable regulations and guidelines are being followed. These visits will ensure that the facilities remain acceptable, the investigational plan is being followed, the IRB and local authorities have been notified of approved investigational plan changes as required, complete records are being maintained, appropriate and timely reports have been made to the sponsor and/or its designees and the IRB, and the investigator is carrying out all agreed upon activities.

An annual report will be generated beginning one year after the first enrollment and will include the following:

- A list and summary of adverse events;
- Whether adverse event rates are consistent with pre-study assumptions;
- A summary of recruitment and retention and reason for dropouts;
- Whether the study is on track to be completed and accomplish the stated aims.

## *Confidentiality:*

Information about study subjects will be kept confidential and managed according to the requirements of the Health Insurance Portability and Accountability Act of 1996 (HIPAA). Those regulations require a signed subject authorization informing the subject of the following:

- What protected health information (PHI) will be collected from subjects in this study
- Who will have access to that information and why
- Who will use or disclose that information
- The rights of a research subject to revoke their authorization for use of their PHI

In the event that a subject revokes authorization to collect or use PHI, the investigators, by regulation, retains the ability to use all information collected prior to the revocation of subject authorization. For subjects that have revoked authorization to collect or use PHI, attempts should be made to obtain permission to collect at least vital status (i.e. that the subject is alive) at the end of their scheduled study period.

#### *Data Collection and Management*

##### Case Report Forms—

Qualified study staff at the investigational site will perform primary data collection. Electronic case report forms (eCRFs) will be used to collect all subject data during the study. The investigator is responsible for the accuracy and completeness of all data on the eCRFs. Lead site personnel will review completed eCRFs at regular intervals throughout the study.

Information on the eCRFs will be compared to information originally recorded on source documents related to the study. Information on the eCRF must match the same information on the source documents or a data query will be issued. All eCRFs will be reviewed for completeness, validity, and consistency. Queries will be generated and resolved with the sites and all protocol deviations will be recorded on the eCRF.

##### Source data—

Source data is all information, original records of clinical findings, observations, or other activities in a clinical trial necessary for the reconstruction and evaluation of the trial. Source data are contained in source documents. Examples of these original documents, and data records include: hospital records, clinical and office charts, laboratory notes, memoranda, subjects' diaries or evaluation checklists, pharmacy dispensing records, recorded data from automated instruments, copies or transcriptions certified after verification as being accurate and complete, microfiches, photographic

negatives, microfilm or magnetic media, x-rays, subject files, and records kept at the pharmacy, at the laboratories, and at medico-technical departments involved in the clinical trial.

[figure not shown]
### **7.3. Interim analyses**

We anticipate two interim analyses after 50% and 75% of the sample size are recruited, but the exact timing will be at the discretion of the DSMB. Analyses will be performed by the study statistician and presented to the DSMB, which will make recommendations regarding further conduct of the trial. At their first meeting, the DSMB will establish thresholds and rules for trial stoppage based on safety and efficacy limits. Although early stopping decisions cannot be based purely on a mathematical stopping rule, we will use the Haybittle-Peto stopping rule as a guide. Under this rule, the interim analyses of the primary outcome would have to demonstrate an extreme difference between groups ( $P < 0.001$ ) to justify stopping early for efficacy. This rule has the advantages that the exact number of interim analyses need not be specified in advance and the overall type I error is preserved at 0.05; therefore, sample size adjustment for multiple testing is not needed.

## 8. Study Administration

As a multicenter trial with experienced collaborating investigators, governance will be shared rather than directed by a highly centralized and hierachal structure. The Coordinating Center will be located at Indiana University and the Data Management Center will be located at Washington University in St Louis. All the investigators will form the Steering Committee, chaired by the PI.

**Figure 4:** Trial administrative structure

Coordinating Center/Lead Site, Indiana University, will be responsible for:

- Maintaining the study protocol and making revisions
- Updating the site operations manual as needed
- Performing overall management and coordination of the intervention and measurements
- Ensuring all Institutional Review Board requirements are up to date at all sites
- Over-seeing and assisting with recruitment
- Providing training and support for data instruments and quality assurance and control

- Coordinating progress reports to the data management center at WashU

*The Data Management and Analysis Center, WashU, will be responsible for:*

- Creation of randomization sequence
- Creation of the database and extraction tools
- Data cleaning, outlier detection, and preparation for analysis
- Primary analyses of interim data
- Additional analyses as requested by the DSMB or Coordinating Center
- Primary intention-to-treat analyses
- Planned secondary analyses

*Participating Clinical Sites will be responsible for:*

- Screening and recruiting participants
- Determining participant eligibility
- Designating group assignment as specified by central randomization
- Data entry
- Developing site-internal procedures and training/certifying staff members as appropriate
- Assuring compliance with Institutional Review Board requirements
- Responding to Quality Assurance reports
- Maintaining good recruitment rate
- Reviewing and reconciling study data
- Entering participant data into study database and responding to data cleaning requests
- Submitting inquiries on procedural issues to the Coordinating Center
- Responding to requests for data regarding interim and final analyses and data safety

*Steering Committee*

The Steering Committee (SC) for the trial will be chaired by The PI. The SC will comprise the PI ([name]) and the site-PIs (Drs. [name], [name], [name], and [name]) and Health Economist Co-I ([name]). The functions and responsibilities of the SC are:

- Decision making regarding participant eligibility and study end points
- Publication and presentation guidelines
- Authorship determination
- Consideration and approval of ancillary studies
- Addressing scientific or operational matters as they arise

The investigators are all experienced and most have collaborated in prior studies. Any issues will be addressed at regular Steering Committee conference calls and yearly scheduled meetings to coincide with the annual Society for Maternal Fetal Medicine meeting attended by most investigators.

#### *Data Safety and Monitoring Board (DSMB)*

A DSMB has been established to ensure objective oversight of the trial's safety and conduct. Members of the Data Safety and Monitoring Board will be [name], MSCE (Chair); [name], MSCI; and [name], who represent appropriate expertise including epidemiology, infectious disease, obstetrics, clinical trials, and biostatistics. Members are not involved in any aspect of the trial operation. They will provide oversight to assure that the trial accrues at a sufficient rate and that the safety and privacy of all study participants is assured. The DSMB will hold conference calls every six months to review study progress and monitor adverse events. The DSMB will be confidentially briefed by the study statistician before each meeting regarding study progress, and study outcomes. That information will be available to the study investigators once disclosed by the DSMB. The DSMB will issue a written report to the investigators after each meeting outlining any study issues and needed actions.

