#### **4.4. Randomization**

Women will only be randomized once the decision is made to do a cesarean. A confidential web-based randomization sequence will be prepared by using blocks of variable sizes, stratified by study site, BMI category (30-39.9 and  $\geq 40$  kg/m^2) and scheduled/non-labor versus unscheduled/labor cesareans. The randomization sequence will be maintained centrally by the study statistician. The patient's group assignment will be revealed once basic information including confirmation of the inclusion criteria are submitted online.

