#### **4.8. Outcome Measures**

##### **4.8.1 Primary Outcome**

Superficial or deep surgical site infections as defined according to the CDC's National Healthcare Safety Network criteria. Diagnosis will be made by the treating physician and reviewed and validated centrally by the PI against the *CDC's National Healthcare Safety Network Definitions of Surgical Site Infections* and blinded to intervention group

A **superficial incisional (or wound) SSI** must meet the following criteria: Infection occurs within 30 days after the operative procedure AND involves only skin and subcutaneous tissue of the incision AND patient has at least one of the following: i) purulent drainage from the superficial incision; ii) organisms isolated from an aseptically obtained culture of fluid or tissue from the superficial incision; iii) at least one of the following signs or symptoms of infection: pain or tenderness, localized swelling, redness, or heat, and superficial incision is deliberately opened by surgeon, and is culture-positive or not cultured (a culture-negative finding does not meet this criterion); iv) diagnosis of superficial incisional SSI by the surgeon or attending physician.

A **deep incisional (or wound) SSI** must meet the following criteria: Infection occurs within 30 days after the operative procedure AND involves deep soft tissues (e.g., fascial and muscle layers) of the incision AND patient has at least one of the following: i) purulent drainage from the deep incision but not from the organ/space component of the surgical site; ii) a deep incision spontaneously dehisces or is deliberately opened by a surgeon and is culture-positive or not cultured when the patient has at least one of the following signs or symptoms: fever ( $>38^{\circ}\text{C}$ ), or localized pain or tenderness (a culture-negative finding does not meet this criterion); iii) an abscess or other evidence of infection involving the deep incision is found on direct examination, during reoperation, or by histopathologic or radiologic examination; iv) diagnosis of a deep incisional SSI by a surgeon or attending physician.

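### The protocol lets interim study outcomes reach the investigators once the DSMB discloses them, with no limit to pooled data or to a stopped or completed trial

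*Combined protocol and SAP*

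**What the plan says.** The DSMB part of Section 8 (Study Administration) contains two consecutive sentences: "The DSMB will be confidentially briefed by the study statistician before each meeting regarding study progress, and study outcomes", and then "That information will be available to the study investigators once disclosed by the DSMB". The next sentence separately provides for a written DSMB report to the investigators on issues and required actions. Meetings are six-monthly: "The DSMB will hold conference calls every six months to review study progress and monitor adverse events".

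Section 7.3 (Interim analyses) plans two formal looks: "We anticipate two interim analyses after 50% and 75% of the sample size are recruited". On stopping it says "we will use the Haybittle-Peto stopping rule as a guide", with a threshold of P < 0.001 for efficacy. It sets no rule on who may see interim results.

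On who the investigators are and what they decide, Section 8 says that all of them form the Steering Committee, chaired by the PI. Its listed functions include "Decision making regarding participant eligibility and study end points". Section 5.3 (Data Processing) adds that the analysis plan is still to be finalized by the Steering Committee and approved by the DSMB, without giving a date.

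On masking and ascertainment, Section 4.4 states: "The patient's group assignment will be revealed once basic information including confirmation of the inclusion criteria are submitted online". Section 4.8.1 states: "Diagnosis will be made by the treating physician and reviewed and validated centrally by the PI". The same sentence ends by saying that this review is blinded to intervention group. Under the definitions in 4.8.1, a diagnosis by the surgeon or attending physician is by itself enough for a superficial or a deep SSI.

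**The concern.** In the DSMB text, the information that may be released is what the statistician has just briefed, and that includes study outcomes. The written report already covers recommendations, so the release sentence goes further than the usual feedback from a DSMB.

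Knowledge of an interim trend could bias the rest of the trial by two routes.

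- **Decisions.** People who may receive interim outcomes also decide on end points and eligibility and finalize the analysis plan. Decisions taken with knowledge of the trend are no longer independent of the data.
- **Ascertainment.** The trial is not masked at the sites, and part of the primary outcome rests on clinical judgement. A clinician who believes that one arm is doing better may be slower to call an SSI in that arm. Treating physicians need not be investigators, so this route is indirect.

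**Working it through.** **1. What may be released, and when.** The two DSMB sentences were set against every other place that could restrict them.

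| Place | Does it restrict release? |
|---|---|
| Section 8, DSMB | Briefing is confidential and release waits for the DSMB; no limit on content (pooled or by arm) or on timing |
| Section 8, written report | Covers issues and actions; separate from the release sentence |
| Section 7.3 | Stopping thresholds and recommendations; nothing on confidentiality |
| Section 5.3 | Steering Committee finalizes the analysis plan; no requirement that this precede interim results |
| Section 4.8.1 | Central validation blinded to group; nothing on access to aggregate results |

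The text therefore permits release of interim outcomes during recruitment. It does not require it.

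**2. How much of the trial would be exposed.** With 2850 women, release at the 50% look leaves 2850 − 1425 = 1425 still to be recruited. Release at the 75% look leaves 2850 − 2137.5, about 712.

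**3. The plan's own sample size.** Inputs from Section 6.1.1 and Table 4: 10% versus 7%, two-sided 5%, 80% power, 5% loss.

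n per arm = [1.96·√(2·0.085·0.915) + 0.842·√(0.10·0.90 + 0.07·0.93)]² / 0.03² ≈ 1356

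The total is 2712, and 2712/0.95 = 2855. With unpooled variance the total is 2706, and 2706/0.95 = 2849. The stated 2850 reproduces and is not in question. Evaluable women per arm: 2850 × 0.95 / 2 ≈ 1354.

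**4. Hypothetical size of an ascertainment bias.** The assumptions below are not in the documents: no true effect, 10% risk in both arms, release after a fraction f of recruitment, and a relative under-diagnosis u in the NPWT arm only, from then on, which survives central review.

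- Observed NPWT risk: pN = 0.10·[f + (1 − f)(1 − u)]; control pC = 0.10; d = pC − pN.
- s0 = √(2·p̄(1 − p̄)/1354), where p̄ is the mean of pN and pC; s1 = √([pC(1 − pC) + pN(1 − pN)]/1354).
- False-positive probability (two-sided) = 1 − Φ[(1.96·s0 − d)/s1] + Φ[(−1.96·s0 − d)/s1].

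Example, f = 0.5 and u = 0.10: pN = 0.095, d = 0.005, s0 ≈ s1 ≈ 0.0114. The two terms are 1 − Φ(1.521) = 0.0641 and Φ(−2.399) = 0.0082, which sum to 0.0723.

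| Release at | u | Apparent RR | SSIs missed (1354·d) | False positives |
|---|---|---|---|---|
| 50% | 5% | 0.975 | 3.4 | 5.5% |
| 50% | 10% | 0.95 | 6.8 | 7.2% |
| 50% | 20% | 0.90 | 13.5 | 14.4% |
| 75% | 5% | 0.9875 | 1.7 | 5.1% |
| 75% | 10% | 0.975 | 3.4 | 5.5% |
| 75% | 20% | 0.95 | 6.8 | 7.2% |

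**5. Does the stopping rule help?** With looks at 50%, 75% and 100% and two-sided levels of 0.001, 0.001 and 0.05, simulation gives an overall type I error of about 0.050. That is control of repeated testing on unbiased data. It does nothing about a shift in how events are diagnosed, or about decisions taken with knowledge of the trend.

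**The case against.** The sentence can be read as a restriction. The briefing is confidential, and nothing is available until an independent board chooses to disclose it. Release is not obligatory, no time is set, and by-arm data are not mentioned. A reader might infer that comparative results go to the investigators every six months. The documents do not support that: the six-monthly calls are for progress and adverse events, and the planned comparisons of the primary outcome belong to the two looks in Section 7.3. What stands against the sentence is that it leaves disclosure open where a protocol would normally close it. No DSMB charter is among the documents, so whether one closes it is unknown.

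A reader might also infer that the PI validates SSIs knowing the allocation. Section 4.8.1 says the opposite. The blinding is a real safeguard, but a partial one. It applies to diagnoses already made by clinicians who are not described as masked. No section provides for review of cases that were never diagnosed, and a criterion met by a clinician's diagnosis alone is hard to overturn.

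Nor do the documents say that treating physicians are investigators or would be told of interim outcomes. Some may be; the ascertainment route depends on it.

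The objection also holds for recruitment. A change in who is approached acts before a central, web-based assignment in variable blocks, so it would alter case mix and not directly the comparison between arms. The Steering Committee's role in end points is a general governance line, and the primary end point is defined in 4.8.1, but the open analysis plan in Section 5.3 keeps that route alive.

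Finally, the bias figures assume immediate uptake at all sites and do not separate the effect of release from the detection bias that any unmasked trial may carry. The fix would not remove the latter.

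**Conclusion.** The point holds as a defect in the rule for access to interim data. The protocol permits interim study outcomes to reach people who decide on end points, eligibility and the analysis plan, in a trial unmasked at the sites with a partly judgement-based primary outcome. Harm arises only if the DSMB discloses comparative results before the trial ends.

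The size of any bias cannot be derived from the documents. On the stated assumptions, false positives range from about 5.1%, close to nominal, for a small shift after a late release, to 14.4% for a 20% shift after release at half recruitment. A reader might take the upper figure as the trial's actual error rate; it is only the worst corner of an assumed range. The decision route has no figure. The change is worth making because it costs almost nothing and blinded validation covers only part of the risk.

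**What to change.** Replace the release sentence in the DSMB part of Section 8 with text to this effect:

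- Until the trial is stopped or the database is locked, outcome data by arm stay with the DSMB and the statistician who reports to it.
- Until then, investigators receive only the DSMB's recommendation and pooled (not by-arm) information on accrual, retention and safety.
- Steering Committee decisions on end points, eligibility and the analysis plan are made without access to by-arm data.

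Any DSMB charter should carry the same wording, so that it and the protocol agree. The cost is a few sentences. No patients, staff or change in sample size are needed, so this is a free improvement.
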